9 REPORTING ADVERSE EVENTS

9.1 Adverse Events

For this protocol, a reportable AE is any untoward medical occurrence (e.g. sign, symptom, illness, disease or injury) in a patient administered the IP or other protocol-imposed intervention, regardless of attribution. This includes:

- AEs not previously observed in the patient, that emerge during the study.
- Pre-existing medical conditions judged by the Investigator to have worsened in severity or frequency or changed in character during the study.
- Complications that occur as a result of non-drug protocol-imposed interventions.

An adverse drug reaction is any AE for which there is a reasonable possibility that the IP caused the AE. "Reasonable possibility" means there is evidence to suggest a causal relationship between the IP and the AE.

	MSK-003	Page 30
---	---------	---------

Whenever possible, it is preferable to record a diagnosis as the AE term rather than a series of terms relating to a diagnosis.

All non-serious AEs, even those which began under Protocol MSK-002, will be reported from the end of the double-blind study (MSK-002) through the termination visit or at the early termination visit and will be recorded on the AE page of the eCRF. All SAEs will be reported. The criteria for determining, and the reporting of SAEs is provided in Section 9.2.

The Investigator should follow all unresolved AEs until the events are resolved or stabilized, the patient is lost to follow-up, or it has been determined that the study treatment or participation is not the cause of the AE. Resolution of AEs (with dates) should be documented on the appropriate CRF page(s) and in the patient's medical record.

The Investigator responsible for the care of the patient or qualified designee will assess AEs for severity, relationship to IP, and seriousness (refer to Section 9.2 for SAE definition). Severity (as in mild, moderate or severe headache) is not equivalent to seriousness, which is based on patient/event outcome or action criteria usually associated with events that pose a threat to a patient's life or functioning. Seriousness (not severity) serves as a guide for defining regulatory reporting obligations.

The Investigator will determine the severity of each AE using grades defined in Table 3 (the event will be recorded on the source documents and AE CRF). Events that are Grades 4 and 5 are serious events and require completion of both an SAE form and AE CRF.

Table 1 Categories of Severity of Adverse Events

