9.2 Serious Adverse Events

A serious adverse event is any untoward medical occurrence that at any dose meets 1 or more of the following criteria:

- Is fatal
- Is life threatening
 - *Note: Life-threatening refers to an event that places the patient at immediate risk of death. This definition does not include a reaction that, had it occurred in a more severe form, might have caused death*
- Requires or prolongs in-patient hospitalization

	MSK-003	Page 33
---	---------	---------

- Results in persistent or significant disability or incapacity
- Is a congenital anomaly or birth defect, that is, an AE that occurs in the child or fetus of a patient exposed to IP prior to conception or during pregnancy
- Is an important medical event or reaction.

The reporting period for SAEs begins after informed consent is obtained for the current MSK-003 study and continues through 4 weeks after the last visit.

Any SAE, whether or not considered related to study drug, must be reported within 24 hours of knowledge of the event by forwarding (fax, email) the study-specific SAE Report Form to Catalyst. The Investigator should not wait to collect information that fully documents the SAE before notifying Catalyst. As additional information becomes available, including but not limited to the outcome of the SAE and any medication or other therapeutic measures used to treat the event, it must be reported within 24 hours in a follow-up report.

The Investigator should follow all unresolved SAEs until the events are resolved or stabilized, the patient is lost to follow-up, or it has been determined that the study treatment or participation is not the cause of the AE. Resolution of AEs (with dates) should be documented in the CRF and in the patient's medical record.

For some SAEs, Catalyst may follow up by telephone, fax, email, and/or a monitoring visit to obtain additional case details deemed necessary to appropriately evaluate the SAE report (e.g. hospital discharge summary, consultant report, autopsy report).

At the last scheduled visit, the Investigator should instruct each patient to report any subsequent SAEs that the patient's personal physician(s) believes might be related to prior study treatment.

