3.3 Safety Analysis

3.3.1 *General*

All safety summaries will be presented overall for the safety population. The evaluation will take into account the recorded adverse events (AE), clinical laboratory tests, vital signs, physical exam, ECG assessments and concomitant medications.

3.3.2 *Adverse Events*

Since patients started taking study medication before enrolled the study, all AE reported are considered as treatment-emergent adverse events (TEAE).

Tabular summaries will be provided by indication for the number and percentage of patients with:

- Any TEAE by SOC and PT. This summary will include the number of unique events reported.
- Any study drug-related TEAE by SOC and PT
- Any TEAEs by SOC, PT and maximum severity
- Any treatment-emergent serious adverse event (TESAE) by SOC and PT
- Any TEAE that results in patient discontinuation from the study by SOC and Preferred Term (PT)

A listing of all adverse events will be provided. In addition, separate data listings will be presented for the following:

- Patient deaths

- Serious Adverse Events (SAEs)
- Listing of Grade 3 (Severe) or Grade 4 (Life-threatening) AEs
- Listing of AEs leading to study discontinuation

3.3.3 *Vital Signs*

A summary of values and changes from Baseline will be provided by vital signs parameter and visit of at 3, 6, 9, 12, 15, 21, 27, 33 and 39 months.

3.3.4 *Electrocardiogram (ECG)*

Each over-read ECG interval and change from baseline in each interval will be summarized descriptively by visit at 3, 6, 9, 12, 15, 21, 27, 33 and 39 months

Treatment-emergent cardiac abnormalities, as well as the overall interpretation, will be summarized. Treatment-emergent ECG findings considered by the investigator to be clinically significant will be presented only in a listing.

3.3.5 *Clinical Laboratory Assessments*

A summary of laboratory values and changes from Baseline will be provided by test and visit of at 3, 6, 9, 12, 15, 21, 27, 33 and 39 months. In addition, laboratory measures out of range or abnormal will be presented for each visit. Values deemed clinically significant by the Investigator will not be summarized, but will be presented in a listing.

3.3.6 *Physical Examinations*

The number and percent of patients with physical examination abnormalities will be summarized by body system and visit of at 3, 6, 9, 12, 15, 21, 27, 33 and 39 months.

3.3.7 *Concomitant Medications*

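### Protocol Section 9.2 lets follow-up of an unresolved SAE end once it is judged unrelated, so outcome and worst grade can be incomplete for those events

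*Protocol*

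**What the plan says.** Protocol Section 9.2 treats intake and follow-up of SAEs differently.

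- **Intake does not depend on cause.** "Any SAE, whether or not considered related to study drug, must be reported within 24 hours of knowledge of the event". The reporting period runs from MSK-003 consent to 4 weeks after the last visit.
- **Follow-up does.** The duty to follow an open SAE ends when it resolves or stabilises, or when contact with the patient is lost. A third condition also ends it: "or it has been determined that the study treatment or participation is not the cause of the AE". Any one of the three is enough. Section 9.1 has the same rule for AEs in general.
- **Later information** is covered by a sentence that begins "As additional information becomes available, including but not limited to the outcome of the SAE" and requires a follow-up report within 24 hours.
- **After participation ends**, Section 9.2 asks the investigator to notify the sponsor of a death or SAE only where a link to earlier study treatment is suspected.

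On the analysis side, SAP 3.3.2 plans a table of "Any TEAEs by SOC, PT and maximum severity", a listing of deaths and a listing of Grade 3 or Grade 4 events. SAP 3.1.3 rules out imputation.

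**The concern.** Every SAE enters the database whatever its cause, but the duty to find out how it ended depends on a causality judgement. Once an SAE is called unrelated, nobody is obliged to seek its later course, and that later course is also the information that might change the judgement.

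Safety is the primary endpoint, and SAP 3.6 has dropped the efficacy analysis, so safety is what this study will deliver. If an SAE is frozen at its last known grade, the recorded worst grade can be at or below the true one but never above it. The loss would also be selective, falling on events judged unrelated.

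**Working it through.** The plan states no figure on this point. The check sets the rules side by side, then gives the weight of a single event.

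**1. Does the clause depend on cause?** Yes. The three stopping conditions in Section 9.2 are alternatives, so a finding of no causal link is enough while the event is still open. The section does not say who makes the finding or when, and does not require it to be revisited.

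**2. What other text still secures the outcome?**

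| Provision | What it covers | What it leaves open |
|---|---|---|
| 24-hour follow-up report (9.2) | Outcome information on any SAE, related or not | Applies to information that reaches the site; does not require it to be sought |
| Sponsor queries (9.2) | Discharge, consultant and autopsy reports, with no causality limit | Optional, and only for some SAEs |
| AE/SAE review at each visit and at End of Study (11.2, 11.2.1; Table 1 footnote g covers early termination) | Patients still attending | Nothing scheduled after early termination; visits are 6 months apart after Month 15 |
| A fatal event is itself an SAE (9.2); Grades 4 and 5 need an SAE form and an AE CRF (9.1) | Worsening or death known to the site within the reporting period | Worsening the site never learns of, or that occurs after 4 weeks |

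The gap is therefore mainly a patient who leaves the study with an open SAE judged unrelated. Section 8.2.3 lists a serious AE among the reasons for withdrawing a patient from study treatment.

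**3. Deaths.**
- Up to 4 weeks after the last visit, a death known to the site must be reported whatever its cause.
- After that, two rules act together. The follow-up clause has already ended the duty to pursue the SAE, and the post-participation paragraph asks for notification only where a link to treatment is suspected. A later death from an SAE judged unrelated then has no required collection route.

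**4. Which outputs can move?** Take a Grade 3 SAE that later becomes Grade 4 or 5 unobserved.

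| Output | Changes? |
|---|---|
| Patients with any serious TEAE (SAP 3.3.2; T08) | No; the event was counted at onset |
| Incidence of TEAEs of Grade 3 or higher (SAP 2.2.1) | No; already counted |
| Grade 2 or higher (T10) | No |
| Inclusion in the Grade 3-or-higher listing (DL06c) | No |
| Maximum severity by SOC and PT (SAP 3.3.2) | Yes; stays at Grade 3 |
| Grade 4 entries in the Grade 3/4 listing (SAP 3.3.2) | Yes; shown as Grade 3 |
| Listing of deaths (SAP 3.3.2) | Only by the route in step 3 |

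Starting from Grade 3 is reasonable because the Protocol's severity table places hospitalisation, disability and medically significant events there, which matches most of the SAE criteria. No planned table summarises SAE outcome.

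**5. Weight of one event.** Assume the planned numbers are reached: 60 MuSK-MG and 10 AChR-MG patients (Protocol synopsis), analysed separately. With exact 95% limits, the upper limit for 0/n is 1 − 0.025^(1/n), and the lower limit for 1/n is 1 − 0.975^(1/n). The upper limit for 1/n is the 0.975 quantile of Beta(2, n − 1).

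| Group | No death recorded | One death recorded |
|---|---|---|
| MuSK-MG, n = 60 | 0%, upper limit 5.96% | 1/60 = 1.67% (0.04% to 8.94%) |
| AChR-MG, n = 10 | 0%, upper limit 30.85% | 1/10 = 10% (0.25% to 44.5%) |

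This shows only what one missed death would weigh. It does not estimate how often that would happen.

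**The case against.** The strongest reply is that Section 9.2 already does most of the work. Any SAE is reportable whatever its cause, a fatal event is an SAE in its own right, known outcomes must be forwarded without regard to relatedness, and the sponsor may request autopsy and discharge reports. The Not Related category on grounds of another etiology also sets a real threshold: there must be no evidence or argument pointing to the drug. An event explained equally well by something else is Possibly Related and must still be followed. Nothing in the documents shows that such judgements are made hastily.

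Most of this stands, and it rules out three stronger readings.

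- **That deaths in general go missing because of this clause.** Deaths known to the site within the reporting period are protected. The later gap needs the post-participation condition as well.
- **That SAE incidence is biased.** Events are counted at onset, so it is not. There is one treatment and no comparator, so the issue is incomplete ascertainment, not imbalance between arms.
- **That the background data give the size.** A reader might use the 7 of 12 deaths in Protocol Section 6.2 that were not considered related. Those come from other studies, published reports and surveillance. Four of the seven were inferred from what an author did not say. A death also has a known outcome, so the figure says nothing about unresolved SAEs here.

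The reply does not close the gap itself. The follow-up report covers information that arrives, sponsor queries are optional, and visits protect only patients who keep attending.

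**Conclusion.** The point holds in a limited form and should be fixed. Section 9.2 makes active follow-up of an open SAE depend on causality, so outcome, resolution date and worst grade can be selectively incomplete for SAEs judged unrelated, chiefly after a patient leaves. Any resulting error lowers recorded severity. It can reach the maximum-severity table and the Grade 4 entries, and the deaths listing only for deaths more than 4 weeks after the last visit.

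The size cannot be estimated, because the documents give neither an expected number of SAEs nor a usable share judged unrelated. The conclusion rests on the wording of the rule and on one assumption: that some sites will stop where the protocol allows them to. It matters despite the modest reach because safety is the primary endpoint, the groups are small and missing data are not imputed.

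**What to change.** - **Follow-up clause, Section 9.2:** delete the causality condition for SAEs, so that each reported SAE is followed until it resolves, stabilises, proves fatal or the patient is lost to follow-up. Require a final outcome and worst grade for each, and re-assessment of causality once the outcome is known.
- **Post-participation paragraph, Section 9.2:** for an SAE already reported and still open at the last or early termination visit, collect the outcome, including death, whatever the causality judgement. Without this change the two paragraphs would conflict.
- **Section 9.1:** the present rule can stay for non-serious AEs.

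If an amendment is no longer practical, the sponsor can query outcome and worst grade for every open SAE before the single database lock planned in SAP 3.4.

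The cost is a short protocol amendment and a few more follow-up contacts for unresolved SAEs judged unrelated.

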Study Assessment or Event	Screening and Enrollment *	Study Month ± 1 week									
		3	6	9	12	15	21	27	33	39	End of Study ^g
Informed consent ^a	x										
Inclusion/Exclusion	x										
Complete physical exam ^b	x	x	x	x	x	x	x	x	x	x	x
Vital signs	x	x	x	x	x	x	x	x	x	x	x
12-Lead ECG	x	x	x	x	x	x	x	x	x	x	x
Clinical laboratory tests ^c	x	x	x	x	x	x	x	x	x	x	x
Pregnancy test ^d	x	x	x	x	x	x	x	x	x	x	x
Amifampridine Treatment	x	x	x	x	x	x	x	x	x	x	x
MG-ADL		x	x	x	x	x	x	x	x	x	x
Dispense IP ^e	x	x	x	x	x	x	x	x	x	x	x
IP Accountability		x	x	x	x	x	x	x	x	x	x
Adverse events/SAEs ^f	x	x	x	x	x	x	x	x	x	x	x
Concomitant medications	x	x	x	x	x	x	x	x	x	x	x

^a Informed consent must be obtained before any study procedures are performed.

^b Complete physical examination includes evaluation of all major body systems, including weight at all visits (Section 9.6.6).

^c Clinical laboratory tests include serum chemistry, hematology, and urinalysis.

^d Urine pregnancy tests will be obtained from female patients of childbearing potential.

^e Pharmacist will dispense sufficient amount of medication until the next clinic visit. All unused medication must be returned to the clinic for drug accountability.

^f SAE reporting commences after informed consent is signed. Non-serious adverse event reporting commences after the first dose of study drug for the current Long-Term Study.

^g End of Study or early termination visit if the last visit does not coincide the scheduled 3- or 6-month visit.

*These data may be obtained from Study MSK-002. If data not available, then the assessment should be repeated.

	MSK-003	Page 21
---	---------	---------

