The Investigator should notify Catalyst of any death or SAE occurring at any time after a patient has discontinued, or terminated study participation, if felt to be related to prior study treatment. Catalyst should also be notified if the Investigator should become aware of the development of cancer, or of a congenital anomaly, in a subsequently conceived offspring of a patient that participated in this study.

Reporting of SAEs to the IRB/IEC/REB will be done in compliance with the standard operating procedures and policies of the IRB/IEC/REB and with applicable regulatory requirements. Adequate documentation must be provided showing that the IRB/IEC/REB was properly and promptly notified as required.

	MSK-003	Page 34
---	---------	---------

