11.2.1 End of Study Visit

Patients will report to the study site at the end of the study and have the assessments and procedures listed below completed. This visit may be incorporated at the scheduled 3-or 6-month visit.

- Assessment of AEs/SAEs;
- Complete physical exam with weight;
- Vital signs (seated position), including SBP, DBP, heart rate, respiration, and body temperature;
- 12-Lead ECG;
- Clinical laboratory tests;
- Urine pregnancy test in females of childbearing potential only;
- Concomitant medications;
- IP accountability;
- MG-ADL

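### In the 4 weeks after the last visit all SAEs are reportable, but Section 9.2 asks patients to report those thought possibly related and no contact is scheduled, so collection is likely to depend on perceived cause

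*Protocol*

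**What the plan says.** Protocol Section 9.2 (Serious Adverse Events) contains four provisions that bear on the time after the last visit.

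- **Window.** SAE reporting starts at MSK-003 consent and "continues through 4 weeks after the last visit".
- **Scope.** "Any SAE, whether or not considered related to study drug, must be reported within 24 hours of knowledge of the event". Within the window the duty is all-cause, and it is triggered when the site learns of the event.
- **Instruction to patients.** At the last scheduled visit the investigator tells each patient to report later SAEs that the patient's "personal physician(s) believes might be related to prior study treatment".
- **Investigator's later duty.** Deaths and SAEs at any time after a patient has discontinued or terminated are to be notified to the sponsor "if felt to be related to prior study treatment".

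On contacts, the final column of Table 1 is defined in its footnote as "End of Study or early termination visit if the last visit does not coincide the scheduled 3- or 6-month visit". Section 11.2.1 describes one site visit: "Patients will report to the study site at the end of the study and have the assessments and procedures listed below completed". Neither lists anything later. Section 8.1 permits telephone or video contact, but places it between the 3- or 6-monthly visits.

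SAP Section 3.5 treats every AE reported in the study as treatment-emergent. SAP Section 4.1 plans tables of serious events (T08) and of events by relationship to treatment (T09). The SAP has no separate rule for events after the last visit.

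**The concern.** The window is defined without regard to cause, but the one route the protocol sets out for patients to report new events in it passes through a causality judgement. That judgement is made by a physician outside the study, whereas Section 9.1 gives assessment of relationship to the investigator or a qualified designee. With no scheduled contact, the site's knowledge of a new event depends largely on what patients volunteer, and they will tend to volunteer what they were told to.

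Safety is the primary objective. Under Section 9.1 collection of non-serious AEs ends at the termination visit, so after that visit new events are collected only through the SAE provisions. If unrelated SAEs are under-reported there, the SAE count falls and the related share among captured events rises. Both feed tables that the SAP plans.

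A second gap adds to this. The instruction is tied to the last scheduled visit, while the window runs from the last visit. A patient who leaves at an unscheduled early termination visit may receive no instruction at all.

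**Working it through.** The plan states no event rate or count for this window, so there is no figure to reproduce. The check is a comparison of texts, followed by arithmetic for scale.

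**Step 1: do the provisions cover the same time?**

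| Provision | Starts | Ends | Filter on cause |
|---|---|---|---|
| SAE reporting period (9.2) | MSK-003 consent | 4 weeks after last visit | none |
| Instruction to patients (9.2) | last scheduled visit | open | personal physician thinks possibly related |
| Investigator's later duty (9.2) | discontinuation or termination | open | felt to be related |
| Scheduled contact (Table 1, 11.2.1) | none after End of Study or early termination visit | – | – |

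The second and third rows overlap the 4-week window, and no wording holds them back until it has closed. The duty to follow unresolved SAEs does run past the last visit, but it concerns events already known.

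**Step 2: size of the window.** Inputs: about 60 MuSK-MG plus about 10 AChR-MG patients (Protocol synopsis), so about 70; and 4 weeks = 28 days (Section 9.2).

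- Person-time = 70 × 28 / 365.25 = 5.4 patient-years. This is an upper figure, because it uses planned maximum enrolment and a full window for everyone.
- Share of a patient's observed time = 28 / (follow-up + 28), with target days from SAP Section 3.1.2:
  - Month 9, day 274: 28 / 302 = 9.3%
  - Month 39, day 1187: 28 / 1215 = 2.3%

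**Step 3: SAEs at stake.** The documents give neither an SAE rate for this population nor the share that would be thought related. Both ranges here are assumptions: 0.05 to 0.20 SAEs per patient-year, and 10% to 50% thought related.

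- Expected SAEs in window = 5.37 × rate: 5.37 × 0.05 = 0.27 to 5.37 × 0.20 = 1.07.
- Missed, if no unrelated event reaches the site = expected × (1 − related share): 0.27 × 0.5 = 0.13 to 1.07 × 0.9 = 0.97.

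**Step 4: effect on the related share among captured events.** Let r be the true related share, let all related events be captured, and let u be the fraction of unrelated events captured. The observed share is r / (r + (1 − r)u).

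| True share r | u = 1 | u = 0.5 | u = 0 |
|---|---|---|---|
| 10% | 10% | 18% | 100% |
| 30% | 30% | 46% | 100% |
| 50% | 50% | 67% | 100% |

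These shares apply to events in the window alone. With about one event or fewer expected there, the effect on whole-study tables would be slight.

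**The case against.** The strongest reply is that the two related-only provisions sit next to each other and read naturally as an open-ended safety net for the time after the 4 weeks, leaving the all-cause window untouched. That may well be the intent. The text does not say so, however: the patient instruction begins at the last scheduled visit with no exemption, and a site that followed it literally would apply the filter inside the window.

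Other parts of the reply stand and limit the point.

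- A reader might infer that patients are told to withhold unrelated events, or that sites need not report them. Section 9.2 says neither. The all-cause duty is unqualified, and sites may learn of events through ongoing care or while following unresolved events.
- The consent form and site reference materials are not available here and may tell patients more. The finding concerns the protocol text.
- The 4 weeks are not the sole follow-up after the last visit. Section 9.2 also covers unresolved SAEs, later related events and cancers the investigator becomes aware of, and Section 9.4 follows pregnancies to outcome.
- A patient who has died reports nothing under any instruction. For deaths, the relevant provisions are the investigator's clause and the absence of a contact.
- A reader might take the window to be off treatment and expect events caused by stopping the drug. The documents do not establish this. Table 1 marks dispensing at End of Study and Section 11.2 provides a 180-day supply at Month 39, while SAP Section 3.1.2 treats Month 39 as the end-of-study visit for completers.
- Passive collection after the last visit is a legitimate design choice. The defect is that the stated scope and the stated instruction disagree.

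**Conclusion.** The point holds as a mismatch within Section 9.2. The window is all-cause, but the patient instruction and the investigator's later duty are limited to related events over the same weeks, and no scheduled contact compensates. Followed as written, collection in these 4 weeks is likely to be incomplete in a way that depends on perceived cause.

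The size is modest: 5.4 patient-years at most, and about one SAE or fewer in the window at the assumed rates. The documents do not support saying that SAEs will certainly be lost, or that the study's SAE and death counts will be materially too low; the realised loss could be nil. The point is still worth correcting because safety is the primary objective, the study is small and descriptive, and the wording is easily repaired.

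**What to change.** **Wording, Section 9.2.** At each patient's last visit, including an early termination visit, instruct the patient to tell the site of any hospitalisation or other serious event in the next 4 weeks, whatever its cause. State that the related-only wording, both for patients and for the investigator's later notices, applies to events after the 4 weeks. This adds no procedures. If it is not accepted as a minor administrative change, Section 13.7 requires ethics committee review of the amendment.

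**Optional contact.** Add one documented telephone or video contact at 4 weeks to Table 1 and Section 11.2.1 to ask about serious events. It would also bring deaths to light, which the wording change alone may not. This is a new contact, since Section 8.1 covers only those between scheduled visits. The cost is one short call per patient plus the amendment.

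**Reconcile.** Bring Table 1 (dispensing at End of Study), Section 11.2 (supply at Month 39) and SAP Section 3.1.2 (Month 39 as end of study for completers) into agreement, so that it is clear whether the 4-week window is on or off treatment.
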